
> Emotional discomfort: It is possible that the study may precipitate discomfort and/or an emotional response when AA-YA answer questions about potentially sensitive topics such as medical mistrust. Further, participants may feel embarrassed about discussing sensitive issues. All participants will be told during the informed consent

> process that their participation is voluntary and that they can chose to stop participating at any time without any consequences. Based on our experiences using similar data collection methods with youth in past studies, the likelihood and seriousness of this risk is minimal and we will strive to create a safe and comfortable environment for all study participants.

All sites have specific policies governing the treatment of human subjects. These policies specify that medical and psychological assistance will be available in the immediate environment in the event a participant should experience any adverse reactions resulting from study procedures.

While participants will be informed that they may refuse to answer any question at any time, responses or reactions to certain questions may indicate distress on the part of the participants. If at any time during the study, a participant divulges that he or she is at risk for harm, including but not limited to being abused or experiencing violence, if harm is suspected or likely, or if the participant states he or she is suicidal/homicidal, measures will be taken to ensure his or her safety. Reporting will be done as appropriate to the situation and the legal statutes, including reporting to child protection agencies or other appropriate agencies and referrals will be provided to appropriate support, counseling, or treatment resources.

- 15.2 N/A
- 15.3 N/A
- 15.4 N/A
- 15.5 N/A
- 15.6 N/A

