Effectiveness Outcomes: Primary effectiveness outcomes are COVID vaccine uptake and completion of series; secondary effectiveness outcomes are VH, confidence, and knowledge, attitudes, and beliefs. We will also collect implementation outcomes, SCT constructs targeted by TT-C, COVID-specific risks and behaviors and pertinent constructs that have been validated in the extant literature on AA-YA (Table 5).

Analyses of Effectiveness Data: We will use logistic regression to determine the effect of treatment arm on the probability of vaccination uptake (yes/no) and COVID vaccine series completion (yes/no) at month three. We will determine whether the overall 2degree-of-freedom test for differences among treatments is statistically significant. If so, we will examine the parameter estimates and standard errors to determine where difference lie between the three arms. We will focus on the odds ratios for comparing the probability of infection in each of the two treatment groups with the probability in the controls. The secondary outcomes of VH, vaccine confidence and vaccine knowledge, attitudes and beliefs will all be assessed using previously validated scale scores, each of which will consist of the continuous sum of responses to a series of questions with Likert scale responses. We will use linear regression models with treatment group as the exposure to determine whether secondary outcomes vary among treatment groups. Lastly, we use the causal mediation framework proposed by Valeri and Vanderweele to understand mechanisms for any intervention effects through each of our hypothesized mediators. We will use the gformula command in Stata which uses the mediational g-formula to estimate the controlled direct, natural direct, and natural mediated (indirect) effects.59

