Missing Data: In sensitivity analyses, we will also use inverse probability of treatment weights (IPTW) to account for missing data and potential differential retention between study arms over the study period. We will weight outcome models using stabilized inverse probability-of-censoring weights that include treatment arm as a predictor to account for differential loss to follow up. Pooled logistic regression models will be used to estimate the numerator and denominator of censoring weights, and weights will be multiplied over time. The denominator will be calculated using a logistic regression model for loss to follow up, including treatment arm. Weights will be stabilized to reduce potential bias from extreme weights. Numerator weights for the stabilized IPTW will be estimated using a logistic regression model for loss to follow up without covariates. Distributions will be examined to ensure weights have a mean of 1; extreme weights that may introduce bias will be trimmed by cutting the top or bottom 1%. Analogous weight will be calculated for missing data, including relevant covariates, and will be multiplied by censoring weights.

Several procedures will be used to conduct data analysis when data for either outcomes or covariates are missing. The first step will be to assess the extent and pattern of missing data. If data are missing for only a few cases, then data analysis will be conducted only on study participants with complete data. However, when such a

> strategy would result in loss of data from a substantial proportion of participants, or if this approach would lead to biased or inaccurate results, then some form of imputation will be performed. The form of imputation used will depend on the nature of the data that are missing. For example, data that are collected repeatedly might be imputed using the "last value carried forward" method; and in some instances, interpolation between neighboring points might also be used.

When the primary endpoint is missing, one data analysis will be conducted using only cases with the endpoint. Subsequent analysis will be done where missing endpoints are imputed. Hot-deck imputation or regression imputation may also be used in this context.

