17.2 We will monitor recruitment and retention rates, site compliance with study procedures, and provide technical assistance for queries and concerns. Encrypted data will be saved on an FSU server, with password protection. We will examine data quality weekly (e.g., missing data, assessment of distributional assumptions, identification of outliers) and before statistical analysis is conducted. Comparability between participants across all three arms will be reviewed. Missing scale data will not be estimated. Comparability between sites and states will be examined. Data will be aggregated for general analysis purposes; however, if significant differences emerge, separate analyses comparing outcomes between sites or states detailing differences will be conducted.

Investigators receiving federal funding must adhere to the Code of Federal Regulations (CFR) to protect research participants and produce reliable study information. Sites participating in research sponsored by the NICHD need to have an internal quality assurance (QA) plan that will identify problems and correct errors in research study records.

Site monitors may visit participating study sites to review a selected portion of the individual participant records, including assent/consent forms, CRFs and supporting source documentation to ensure the protection of study subjects, compliance with the protocol, and accuracy and completeness of records. Regulatory files, as required, will also be inspected to ensure that regulatory requirements are being followed.

The site investigator will make study documents (e.g., consent forms, case report forms) and pertinent hospital or clinic records readily available for inspection by the local IRB, the site monitors, the NICHD, the Office of Human Research Protection (OHRP), or the sponsor's designee for confirmation of the study data.

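### For the secondary scales, Section 17.2 bars estimating missing data while Section 17.1 calls for imputation once loss is substantial or biasing, and nothing says which rule governs

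*Combined protocol and SAP*

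**What the plan says.** Section 17.1 (Analyses of Effectiveness Data) scores every secondary outcome as a scale, "each of which will consist of the continuous sum of responses to a series of questions with Likert scale responses", and compares arms by linear regression on treatment group. It gives no rule for a sum with an unanswered item.

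The Missing Data text in Section 17.1 is general: "Several procedures will be used to conduct data analysis when data for either outcomes or covariates are missing". It then branches:

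- Little missing: "If data are missing for only a few cases, then data analysis will be conducted only on study participants with complete data".
- More missing: if that "strategy would result in loss of data from a substantial proportion of participants", or would give biased or inaccurate results, "then some form of imputation will be performed". As an example, "data that are collected repeatedly might be imputed" by last value carried forward; interpolation is also mentioned.

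The same text plans inverse-probability weighting for loss to follow-up and for missing data, as a sensitivity analysis.

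Section 17.2, in a paragraph on data-quality checks, says without qualification: "Missing scale data will not be estimated".

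Section 15.1 records that participants will be told "they may refuse to answer any question at any time".

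**The concern.** Each secondary outcome is both an outcome in the sense of 17.1 and scale data in the sense of 17.2. Once missingness goes beyond a few cases, one section calls for imputation and the other appears to forbid it. The analysed sample and the estimate for every secondary outcome then depend on which sentence the analyst follows. Section 17.1 starts by looking at the extent and pattern of missing data, sets no threshold for a substantial loss and leaves the imputation method open, so the choice could be made after the data have been seen.

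Last value carried forward raises a further problem. A participant lost before month 1 would have a pre-intervention baseline score entered as the month-3 result.

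A second gap lies at item level. With skipping allowed and no scoring rule stated, a sum with an unanswered item is either missing or too low. If the most hesitant participants skip more, dropping those sums could bias the comparison as well as cost power.

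**Working it through.** **The plan's own sample figure.** Inputs from Sections 6.2 and 17.1: 360 randomized, 180 per arm, about 15% lost. 360 x (1 - 0.15) = 306, or 153 per arm, which matches Exhibit 1. The number lost is 360 - 306 = 54. The detectable differences stated there concern vaccine uptake, which is binary; the documents contain no sizing for the scales.

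**The two rules at the planned loss.** I assume that the scales suffer the same 15% loss as the primary endpoint, since Section 6.2 has follow-up surveys at months 1 and 3 for both arms.

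| Reading of 17.2 | Wholly missing scores | Skipped items |
|---|---|---|
| Covers whole scores | 17.2: about 306 analysed, none imputed. 17.1: up to 360, of which 54 (15%) imputed, if 15% counts as substantial. Conflict. | Not filled in |
| Covers single items only | 17.1 governs. No conflict. | Not filled in; no rule for the resulting sum |

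If only a few cases are missing, both sections lead to complete cases and agree. Whether 54 of 360 is a few or a substantial proportion is undefined, but 15% is hard to call a few.

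**Skipped items, illustration only.** The number of items and the skip rate are not in the documents. Assume k items, each skipped independently with probability q, and assume that one skip voids the sum.

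- Share of sums lost = 1 - (1 - q)^k
- Detectable difference in SD units (80% power, two-sided 0.05) = (1.960 + 0.842) x sqrt(2/n), with n per arm

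| k | q | Sums lost | Left of 306 | Detectable difference |
|---|---|---|---|---|
| any | 0 | 0% | 306 | 0.320 SD |
| 5 | 0.5% | 2.5% | 298 | 0.324 SD |
| 10 | 1% | 9.6% | 277 | 0.337 SD |
| 10 | 2% | 18.3% | 250 | 0.354 SD |
| 20 | 2% | 33.2% | 204 | 0.392 SD |

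Worked line for k = 10, q = 2%: 1 - 0.98^10 = 0.183; n = 153 x 0.817 = 125; 2.802 x sqrt(2/125) = 0.354. Skips concentrated in the same people would lose fewer sums.

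**The case against.** The strongest reply is that the two sections can be read together. Imputation in 17.1 is conditional, and its low-missingness branch agrees with 17.2. The 17.2 sentence sits among data-quality checks and may mean only that single items are not filled in; it may also be a specific exception to a general rule. The scales are described as previously validated, so their sources may carry scoring rules for skipped items. Much of this stands. The conflict is conditional and depends on the reading. But the text supports neither reading over the other, and one reading makes 17.2 the plan for these outcomes while the other leaves them to 17.1. The promise in 17.1 to document deviations in a statistical analysis plan does not help while the planned rule cannot be identified.

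Stronger conclusions are tempting, and the documents do not support them:

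- *That 17.1 always requires missing scale scores to be imputed.* The unconditional imputed analysis applies to the primary endpoint only, and that is not a scale.
- *That the trial will lose a large share of scale scores.* This rests on item counts, skip rates and independence that the documents do not give. Section 15.1 is a general statement about participants' rights and says nothing about how often items are skipped.
- *That bias from missing scale data is ignored.* The planned weighting addresses it as a sensitivity analysis, and reweighting estimates no score, so it is compatible with 17.2.
- *That month-1 scores are certain to be discarded.* The linear-regression sentence names no time point. It plans no repeated-measures term, but it does not exclude month-1 data.

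**Conclusion.** The point holds in a limited form. For the secondary scales, 17.1 and 17.2 give different instructions once missingness is substantial or biasing, provided that 17.2 covers whole scores. The planned 15% loss plausibly reaches that trigger, and the difference is then about 306 observed scores against up to 360 with 54 imputed. This rests on the scales sharing the primary endpoint's loss and on 15% counting as substantial. If 17.2 covers single items only, the conflict disappears, but the documents still give no rule for a sum with a skipped item.

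The item-level loss has no figure that the documents can support. The 10-18% for a 10-item scale is an illustration under independent skips at 1-2%, and it would move the detectable difference from 0.320 to between 0.337 and 0.354 SD. The primary outcome, vaccine uptake and series completion, is not touched by this conflict. The matter should be settled before the secondary outcomes are analysed.

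**What to change.** Make Sections 17.1 and 17.2 agree, with one rule for each level.

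- **Skipped items.** Use each scale's own published scoring rule. Where there is none, prorate (mean of answered items times the number of items) when at least 80% of items are answered; otherwise treat the score as missing.
- **Wholly missing scores.** Do not use last value carried forward. Analyse month-1 and month-3 scores in a mixed model for repeated measures, with arm, visit, arm-by-visit, baseline score and state as covariates. State is the stratification factor in Section 6.2. Baseline is a covariate only and must not also be in the response. The month-3 arm contrast is the estimate.
- **Sensitivity.** Keep the planned weighting.

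A participant with a month-1 score but no month-3 score then contributes without any score being filled in. A participant with neither contributes nothing, and the documents do not say how many of the 54 would fall in each group.

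The cost is revised wording and a standard model on data already being collected. The model relies on a missing-at-random assumption. The 80% threshold is a choice that the documents do not supply, and proration is itself a form of estimation, so the 17.2 sentence must be replaced and cannot simply be left beside it.

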3.3 Acceptance of COVID vaccination is lowest among YA and African Americans (AA). Two highly effective vaccines for COVID were given Emergency Use Authorization (EUA) by the FDA in December, the Moderna and Pfizer, mRNA vaccines. The Moderna vaccine showed 94% and Pfizer 90% efficacy in phase 3 trials. Both vaccines require 2 doses about 3-4 weeks apart. Despite the high efficacy, the rapid development and testing of these vaccines has resulted in public concern around safety of the vaccines. This built on a history of medical mistrust has result in low levels of willingness to take up a vaccine in surveys done among AA populations in the US. Rates of COVID-19 vaccination are currently at 61.8% in Alabama, 64.3% in Georgia, and 82.2% in North Carolina, with rates continuing to be lower among African American populations in southern states. A recent 2022 Health Resources and Services Administration (HRSA) report found that only 54.5% of African American residents in surveyed Georgia clinics accepted their first vaccine dose, 10% lower than the overall state rate and only 34.1%, 34.9%, and 25.1% of Alabama, Georgia, and North Carolina residents, respectively, have accepted a booster. Those who remain unvaccinated may be highly resistant toward accepting vaccination or are overwhelmingly apathetic. Further, lower vaccine acceptance was associated with younger age (18-49 years) in a nationally representative survey conducted in October 2020 among US residents (n=525).19

All aims of this study have been previously reviewed and approved by the University of North Carolina at Chapel Hill IRB. Aims 1 and 2 were completed while the research team was at UNC-CH. By submitting this protocol to Florida State University, we are seeking IRB approval for the RCT (Aim 3) and analysis activities only. The original protocol, study documents, and approval letters are appended in the IRB submission.

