### 6.0 **Procedures Involved**

6.1 This study will consist of three distinct aims to develop and test the TT-C intervention for COVID vaccine hesitant AA-YA. Aims 2 and 3 procedures are premised on the formative data collected in Aim 1.

Aim 3: Conduct a hybrid type 1 effectiveness implementation 2-arm randomized controlled trial with 360 AA-YA from AL, NC, and GA.

6.2 Enrollment: After screening eligible and agreeing to be contacted, eligible responses will be reviewed individually by study staff to determine authenticity and legitimacy. In addition to eligibility criteria, staff will review bot detection values as well as location based on IP address & latitude/longitude. If determined eligible, staff complete the Verification CRF and REDCap will email the individual with a unique consent form link to complete. Once completed, REDCap will send the baseline survey linked to their unique ID in REDCap.

After the baseline survey is complete, study staff will randomize the participant with the Randomization CRF to either the intervention or control group. Based on the study arm, study staff will either email the participant with the developed SOC materials or email the participant with a unique link to create their account for the TT-C app. If SOC, the participant will be compensated at this time.

If participant is randomized to intervention arm, they will be prompted to create their account with the provided link, then will be

> directed to download and login to the TT-C app. Once account creation is confirmed in the administrator portal, study staff will compensate the participant for enrolling.

Randomization: RCT participants will be randomized via block randomization into the control condition and TT-C (remote), each with a balanced 180 participants. Assignment will be stratified by state to achieve balance between intervention and control participants within a given study state.

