### 17.0 Data Management and Confidentiality

17.1 Sample Size Considerations: Sample size calculations were conducted using simulation methods. The simulations: a) Step One: specify probabilities of vaccination and sample sizes for the three treatment groups and draw random samples of the specified sizes from binomial distributions with the specified probabilities treated as binomial parameters; b) Step Two: compare the outcome rates in the three samples using logistic regression and record whether the 2 degree-of-freedom test for differences is statistically significant; c) Step Three: make pairwise comparisons treatment arms using logistic regression; and d) Step Four: Repeat process 1,000 times and calculate power as the proportion of data sets (of 1000) generating statistically significant results.

Power calculations were conducted assuming that dropout would be equivalent across arms, and that approximately 15% would be loss to follow-up; therefore, assuming 250 306 participants will complete the primary endpoint assessment (125 153 per arm). Exhibit 1 depicts graphically the estimated detectable effect sizes (as a difference in proportion receiving any COVID vaccine) we will have 80% power to detect given a sample size of 250306, range of control arm rates of vaccine uptake, and assuming two-sided  $\alpha$ =0.05. If the rate of COVID vaccination in the control arm is between 10-20%, we will have 80% power to detect a difference in vaccination of 1312-146% between arms. If the rate of vaccination in the control arm is higher (30%), we will have 80% power to detect a 1715.5% difference in vaccination rate between arms. The detectable effect size is lowest highest when the control proportion is closer to 50%, but we will still have 80% power to detect a difference of 17.616% if the rate of vaccination in the controls is 50%. We anticipate vaccination rate in the control arm will be low given that vaccines have been available for some time. Therefore, we expect a total sample size of 300 360 will provide sufficient power to detect a clinically meaningful difference in vaccine uptake.

**Exhibit 1.** Estimated detectable effect size with an effective sample size of 306 (153 per arm) and range of possible vaccination rates in the control arm; 80% power and two-sided alpha of 0.05.

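### Section 17.2 lets undefined differences between sites or states trigger separate analyses, while no arm-by-state interaction is planned and the primary model omits the stratification factor

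*Combined protocol and SAP*

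**What the plan says.** Section 17.2, in a paragraph on data quality, says that comparability between sites and between states will be looked at and that data will be pooled for general analysis. The exception is that "if significant differences emerge, separate analyses comparing outcomes between sites or states detailing differences will be conducted". The variable compared, the test and the threshold are not given.

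Section 6.2 on randomization states: "Assignment will be stratified by state to achieve balance between intervention and control participants within a given study state". This balances the arms within each state; it does not fix how many participants each state contributes, and no per-state target is given elsewhere.

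The effectiveness analysis in section 17.1 is a logistic regression of uptake and of series completion at month three on treatment arm. It has no term for state and no arm-by-state interaction. Section 17.1 also mentions a Statistical Analysis Plan, as the place where deviations will be documented and justified. Nothing in the document reviewed supplies a fuller rule for states.

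**The concern.** Two questions are easily confused. One is whether states differ, in who enrols or in how many are vaccinated. The other is whether the app's effect differs between states. Only the second justifies separate conclusions by state, and it is answered by an arm-by-state interaction. A rule that turns on undefined significant differences can be satisfied by the first question alone, and it leaves the choice of what counts to be made after the data are seen.

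At stake are the state-level statements in the report. If the arm comparison is repeated within each state after such a trigger, each test rests on roughly a third of the data. A pattern of significance in one state and not in another could then be reported as a state-specific effect when the true effect is the same everywhere.

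Leaving state out of the primary model is a related gap: the design uses the factor, the analysis does not.

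**Working it through.** **Inputs.** Section 17.1 gives "80% power and two-sided alpha of 0.05" and assumes that "approximately 15% would be loss to follow-up", so 360 × 0.85 = 306 completers, 153 per arm. Its detectable differences are 12 to 14 points for control uptake of 10 to 20%, 15.5 points at 30% and 16 points at 50%. In the text as extracted, old and new figures run together; the newer ones are used here, and they match 153 per arm. Equal enrolment in the three states is an assumption: 153 / 3 = 51 completers per arm per state.

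**Formula.** For n per arm, control rate p1, intervention rate p2 and p̄ = (p1 + p2)/2,

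power = Φ{ [ |p2 − p1|·√n − 1.96·√(2p̄(1 − p̄)) ] / √(p1(1 − p1) + p2(1 − p2)) }.

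**Step 1: the plan's own figures.** For 20% v 34% with n = 153: (0.14 × 12.369 − 1.96 × 0.6279) / 0.620 = (1.732 − 1.231) / 0.620 = 0.808, and Φ = 0.79. Solving for 80% power gives 11.6, 14.2, 15.5 and 15.8 points at control rates of 10, 20, 30 and 50%. The plan's figures reproduce.

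**Step 2: an arm comparison within one state.** For 20% v 34% with n = 51: (0.14 × 7.141 − 1.231) / 0.620 = −0.372, and Φ = 0.355.

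| Control v intervention | 153 per arm | 51 per arm | Range, 25 to 100 per arm |
|---|---|---|---|
| 10% v 22% | 82.0% | 37.8% | 20.8% to 64.0% |
| 20% v 34% | 79.1% | 35.5% | 19.6% to 60.8% |
| 30% v 45.5% | 80.2% | 36.3% | 20.0% to 62.0% |
| 50% v 66% | 81.3% | 37.2% | 20.5% to 63.2% |

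At the exact 80%-power differences the value with 51 per arm is 36.2%. The difference detectable with 80% power in one state rises to 22.4, 25.8, 27.2 and 26.4 points at control rates of 10, 20, 30 and 50%.

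**Step 3: what three such tests would show.** With the same 20% v 34% effect in every state, and power 0.355 in each:
- all three significant: 0.355³ = 0.045
- none significant: 0.645³ = 0.269
- a mixture: 1 − 0.045 − 0.269 = 0.69

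With no effect anywhere, the chance that at least one of three tests is significant is 1 − 0.95³ = 14.3%.

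**Step 4: a level-based trigger against an interaction test.** Both scenarios were simulated with 51 per arm per state and chosen uptake rates that illustrate the logic; they are not forecasts. The level test is a 2-df chi-square of state by outcome.
- Control uptake 10/20/30% and the same odds ratio in every state, (0.34/0.66)/(0.20/0.80) = 2.06: the level test is significant about 96% of the time, and a heterogeneity test of the arm effect about 4%.
- True effects of 0, 14 and 28 points, with overall uptake 27% in each state: the level test is significant about 5% of the time, and the heterogeneity test about 51%.

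A level difference is therefore neither sufficient nor necessary for a difference in effect.

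**Step 5: state in the primary analysis.** In the first scenario, an unadjusted comparison has power of about 75% and a state-stratified one about 77%. With no effect, type I error is about 5% for both. Adjustment gains a little and loses nothing here.

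**The case against.** The strongest reply is textual. Read literally, the clause compares outcomes between sites or states. It does not promise an arm comparison inside each state, so a reader who takes it to announce three small trials goes beyond the text. That stands: the 36%, the 69% and the 14.3% belong only to the within-state reading. That reading is plausible, because the clause is the exception to pooling in a trial whose outcomes are compared by arm, but it is not explicit. On the literal reading the plan still never asks whether the effect varies by state.

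Second, a reader might infer that the trigger carries no information about the app's effect. The document does not support that. The term is undefined: it could mean baseline differences, differences in uptake level, or differences in effect. What can be said is that the trigger is unspecified.

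Third, a reader might infer from section 3.3 ("Rates of COVID-19 vaccination are currently at 61.8% in Alabama, 64.3% in Georgia, and 82.2% in North Carolina") that the trigger will almost always fire. Those are general state rates. The trial enrols hesitant young adults, excludes those with the full series and anticipates low control uptake. The same section gives booster rates of 34.1%, 34.9% and 25.1% for Alabama, Georgia and North Carolina. These lie closer together, put North Carolina lowest, and would make a level test significant only about 31 to 36% of the time with 102 to 120 participants per state. Neither set predicts uptake in this trial, so no firing rate is claimed.

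Fourth, pooling remains the general analysis, so this clause does not alter the primary estimate or its error rate. That also stands and limits the severity.

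**Conclusion.** The concern holds in a bounded form. Section 17.2 makes separate site or state analyses depend on an undefined trigger, no arm-by-state interaction is planned, and the primary model leaves out the factor used to stratify allocation. These follow from the text and need no assumption.

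The numerical cost is conditional on two things: that the clause means arm comparisons within each state, and that enrolment is equal across the three states. Then power is about 36% at the plan's own detectable differences. With uneven states it runs from about 20% (25 per arm) to about 64% (100 per arm), below 80% throughout. Any subset smaller than a state, such as a single site, would have less power than the state it lies in. The 69% chance of a mixed pattern rests on the same two conditions and on a common 20% v 34% effect.

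The matter should be corrected, but it does not threaten the pooled primary result.

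**What to change.** 1. In section 17.1, include state as a covariate in the primary logistic model.
2. In section 17.2, delete the conditional move to separate analyses. Replace it with one prespecified arm-by-state interaction test, labelled exploratory.
3. Report the arm effect in each state with a confidence interval as descriptive results, whatever the comparability checks show, and draw no conclusion from which states reach significance.
4. Keep the pooled analysis as primary, and keep the comparability checks as data-quality checks that do not alter the analysis.

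The cost is wording, two extra parameters for state in the primary model, and an interaction test with low power: about 51% in the simulation above, even for effects as far apart as 0, 14 and 28 points. A non-significant interaction must therefore not be read as evidence that the effect is the same everywhere. No extra participants or data are needed.
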